## **6. GENERAL ANALYSIS DEFINITIONS**

### **6.1 TREATMENTS**

For basic study information on treatments to be administered, assignment of treatment groups, and selection of doses cf. Section 4 of the CTP.

In trial period R (Reference Period) subjects will receive bupropion alone (Reference treatment R) whereas in trial period T (Test Period) bupropion plus BI 1358894 (Test treatment T) will be administered.

In trial period R, each subject will receive:

- 150 mg bupropion hydrochloride administered as sustained release tablet in fed state

In trial period T, each subject will receive:

- Multiple doses of 100 mg BI 1358894 administered once daily on 19 days (Day -14 to Day 5) as tablets in fed state combined with a single dose of 150 mg bupropion hydrochloride on the 15th day of BI 1358894 treatment (Day 1).

**CTP Section 1.2.3:** *The Residual Effect Period (REP) of BI 1358894 is 14 days. The Residual Effect Period (REP) of bupropion is 5 days. This is the period after the last dose with measurable drug levels and/or pharmacodynamic effects is still likely to be present.*

For statistical analysis of AEs, the following analysis phases are defined for each subject. Analysis phases for active treatments are defined separately for Period R and Period T.

Table 6.1: 1 Analysis phases for statistical analysis of AEs, and actual treatment for analysis of laboratory data and vital signs

Study analysis phase		Label	Start	End
Screening 	Screening		Date of informed consent	Date/time of first administration of Bupropion
On treatment	Bupropion		Date/time of first administration of Bupropion	Date/time of first administration of Bupropion + REP (5 days * 24 h) or 12:00 a.m. on day after subject's end of trial termination date, whichever occurs earlier.
Follow-up	F/U Bupropion		Date/time of first administration of Bupropion + REP (5 days * 24 h)	Date/time of first administration of BI 1358894 or 12:00 a.m. on day after subject's end of trial termination date, whichever occurs earlier.
On treatment	BI 1358894		Date/time of first administration of BI 1358894	Date/time of administration of Bupropion (Visit 3) or date/time of last administration of BI 1358894 + REP (14 days * 24 h) or 12:00 a.m. on day after subject's end of trial termination date, whichever occurs earlier.

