On treatment	BI 1358894 + Bupropion		Date/time of administration of Bupropion at Day 1, Visit 3	Date/time of administration of Bupropion (Visit 3) + REP (5 days * 24 h) or 12:00 a.m. on day after subject's end of trial termination date, whichever occurs earlier.
On treatment	BI 1358894		Date/time of administration of Bupropion (Visit 3) + REP (5 days * 24 h)	Date/time of last administration of BI 1358894 + REP (14 days * 24 h) or 12:00 a.m. on day after subject's end of trial termination date, whichever occurs earlier.
Follow-up	F/U BI 1358894		Date/time of last administration of BI 1358894 + REP (14 days * 24 h)	12:00 a.m. on day after trial termination date

 See [Section 6.7](#) for definition of baseline, which will be used in the statistical analyses of safety laboratory data and vital signs.

AE summary tables will present results for the on-treatment phase only. All AEs will be listed.

**CTP Section 7.3.4:** Note that AEs occurring after the last per protocol contact but entered before final database lock will be reported to Pharmacovigilance only and will not be captured in the trial database.

The following AE tables will be provided in the report:

- Section 15.3, Appendix 16.1.13.1.8.1 and 16.1.13.1.8.2 of the CTR displays

In these displays, the on-treatment phase will be analysed (labelled with the name of the study treatment (short label)). Screening will not be included in this analysis.

In Section 15 AE tables (but not in Appendix 16.1.13.1.8.1 and Appendix 16.1.13.1.8.2 AE tables), the following totals will be provided in addition:

- "Total Bupropion", defined as the total over all on-treatment phases involving bupropion
- "Total BI", defined as the total over all on-treatment phases involving BI
- "Total on-trt", defined as the total over all on-treatment phases involving BI and bupropion

Listings of AEs presented in Section 15.4 will display results for the screening, on-treatment phases, and follow-up phases (labelled with the name of the study treatment (short label)).

Safety laboratory data and vital signs will be analyzed based on treatments in the respective treatment period (Period R: Bupropion; Period T: BI + Bupropion) with clear differentiation between baseline (cf. [Section 6.7](#)) and on-treatment measurements. Measurements will be considered on-treatment, if they were taken within the on-treatment phases as defined in [Table 6.1: 1](#).

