## **7.8.2      Laboratory data**

The analyses of laboratory data will be descriptive in nature and will be based on BI standards "Display and Analysis of Laboratory Data" [\(9\)](#).

Analyses will be based on normalised values, which means transforming to a standard unit and a standard reference range. The original values will be analysed if the transformation into standard unit is not possible for a parameter.

Descriptive statistics of laboratory values over time and for the difference from baseline (see [Section 6.7](#)) will be provided. Frequency tables of changes between baseline and last value on treatment with respect to the reference range will be presented by treatment.

Unscheduled measurements of laboratory data will be assumed to be repeat measurements of the most recent scheduled measurement (e.g. for follow-up or confirmation of a particular value). Therefore, unscheduled measurements will be assigned to the planned time point of the previous scheduled measurement. Descriptive statistics will be calculated by planned time point based on the worst value of the subject at that planned time point (or assigned to that planned time point).

Clinically significant abnormal laboratory values are only those identified either in the Investigator's comments or at the Report Planning Meeting at the latest. It is the Investigator's responsibility to decide whether a lab value is clinically significant abnormal or not.

Laboratory data will be compared to their reference ranges. Values outside the reference range as well as possibly clinically significant values will be highlighted in the listings. Possibly clinically significant laboratory values will be listed in Section 15.4.1.

Clinically relevant findings in laboratory data will be reported as baseline conditions (prior to first administration of study treatment) or as AEs (after first administration of study treatment) if judged clinically relevant by the investigator, and will be analyzed as such.

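### SAP 7.8.2 assigns unscheduled labs to the previous scheduled time point with no check for an intervening treatment start, so a value drawn on BI 1358894 can enter the bupropion-alone row

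*SAP*

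**What the plan says.** SAP 7.8.2 sets the rule for unscheduled labs. First, "Unscheduled measurements of laboratory data will be assumed to be repeat measurements of the most recent scheduled measurement". It follows that "unscheduled measurements will be assigned to the planned time point of the previous scheduled measurement". The summary then takes the most abnormal result: "Descriptive statistics will be calculated by planned time point based on the worst value of the subject at that planned time point", which includes values assigned to that time point. The same section plans a second display: "Frequency tables of changes between baseline and last value on treatment with respect to the reference range will be presented by treatment".

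SAP 6.1 says how labs are attributed to treatment. Table 6.1: 1 is headed "Analysis phases for statistical analysis of AEs, and actual treatment for analysis of laboratory data and vital signs", and its BI 1358894 phase starts at the first BI 1358894 dose. The text below the table says that labs are "analyzed based on treatments in the respective treatment period (Period R: Bupropion; Period T: BI + Bupropion") and adds: "Measurements will be considered on-treatment, if they were taken within the on-treatment phases as defined in" that table.

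The flow charts place safety lab B at Day -1, 24:00 and 120:00 in Period R, and at Day -6, Day -1 and 120:00 in Period T. The laboratory entry on Day -14 carries footnote 16, which states that lab B is not taken then.

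**The concern.** The carry-back rule suits a retest: a second draw to confirm a value belongs with the value it confirms. It suits less well a sample prompted by something new after a treatment has started. The protocol foresees such samples. Section 5.2.6.1.4 provides for an unscheduled blood test when symptoms of hepatic injury appear and no results are available, and subjects are asked about AEs at every daily visit from Day -14.

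No set-B lab is taken on Day -14, so the first BI 1358894 dose falls between two laboratory rows with nothing to separate them. If 7.8.2 is programmed as written, a value that arises on BI 1358894 can replace the subject's own 120:00 value in the bupropion-alone row, because the worst value is used. At stake is whether that row of the laboratory table can be read at face value.

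**Working it through.** The plan gives no figure to reproduce, so the check traces the rules through the schedule.

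**Timeline, in hours after the Period R bupropion dose** (21-day interval, Protocol 3.1):
- Period T bupropion: 21 × 24 = 504 h
- First BI 1358894 dose: 504 − 336 = 168 h
- Day -6 lab B: 504 − 144 = 360 h
- Last Period R lab B: 120 h

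**Window at the first BI 1358894 dose.** 360 − 168 = 192 h, which is 192/336 = 57% of the phase before the Period T bupropion dose. It spans eight doses (Day -14 to Day -7). A sample in it is drawn 168 − 120 = 48 h to 360 − 120 = 240 h after the lab it is assumed to repeat. Under the 6-day minimum separation in Protocol 6.2.2 (144 h), this becomes 144 − 120 = 24 h to 144 + 192 − 120 = 216 h.

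**All three treatment starts, set-B parameters:**

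| Treatment start | Lab B before | Next lab B | Window | Row under 7.8.2 | Phase under Table 6.1: 1 |
|---|---|---|---|---|---|
| Period R bupropion | Day -1 | 24:00 | 24 h | Period R Day -1 (pre-dose) | Bupropion |
| First BI 1358894 dose | Period R 120:00 | Day -6 | 192 h | Period R 120:00 | BI 1358894 |
| Period T bupropion | Day -1 | 120:00 | 120 h | Period T Day -1 | BI 1358894 + Bupropion |

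The middle line matters most, because it moves a value into the other treatment period. The third changes the phase, but not the Period T label that SAP 6.1 uses for labs.

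**Parameters outside set B** (for example electrolytes, glucose, the white cell differential, LDH and urinalysis; Table 5.2.3: 1). The previous scheduled value is the screening one, so 7.8.2 sends an unscheduled result to the screening row.

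**Frequency table.** It uses only the last on-treatment value. After the 192 h window, set-B labs follow on Day -6, Day -1 and at 120:00. A value from the window is the last one only if the subject has no later on-treatment lab for that parameter, for example after early discontinuation.

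**Illustrative size (all inputs assumed).** If p is the chance per subject of an unscheduled lab in the 192 h window, the chance of at least one among 18 subjects is 1 − (1 − p)^18. For p = 0, 1, 5 and 10% this gives 0, 17, 60 and 85%. Suppose k of 18 subjects have a usual value of 0.5 × ULN replaced by x × ULN. The row mean then rises by k(x − 0.5)/18:
- x = 2, k = 1, 2, 3: 0.08, 0.17, 0.25 × ULN
- x = 3, k = 1, 2, 3: 0.14, 0.28, 0.42 × ULN

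The shift is zero if no such sample is drawn.

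**The case against.** The strongest reply is that the two rules do different jobs: 7.8.2 chooses a row in a time-point table, and 6.1 decides on-treatment status. Protocol 7.3.4 assigns measurements by the treatment at their planned time, which favours 7.8.2, and SAP section 4 says that the analyses accord with the protocol. This has weight, but it does not settle the matter. Protocol 7.3.4 leaves the detailed assignments to the TSAP, the TSAP's own treatment rule uses the time taken, and labs are presented by period, so a Period R row is read as bupropion alone.

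Second, the answer may lie elsewhere. SAP 6.1 refers technical detail to the ADS Plan, and 7.8.2 says "The analyses of laboratory data will be descriptive in nature and will be based on BI standards". Neither document was supplied, and either may resolve the point. That stands.

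Third, the dosing condition in SAP 7.8.3 is a limited precedent. It keeps the vital-signs -336:00 time point pre-dose and is not a general safeguard. That also stands, although it shows that the plan considered this dose for one kind of measurement.

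A reader might infer that the laboratory tables will routinely contradict each other. They will not: the frequency table takes only the last on-treatment value, so a clash needs a subject with no later on-treatment lab. A reader might also infer that a liver signal could be hidden. The documents do not support that, because listings, flags for possibly clinically significant values, and AE and AESI reporting do not depend on this rule.

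**Conclusion.** The point holds as a minor one. Read literally, SAP 7.8.2 puts some values drawn after a treatment start into the row before it. The clearest case is a set-B value from the 192 h after the first BI 1358894 dose, which would be shown as bupropion alone while SAP 6.1 attributes it to BI 1358894. The visible text does not say which rule governs.

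The effect is confined to descriptive by-time-point laboratory tables and arises only if such a sample is drawn and is the subject's worst value for that row. Baseline is unaffected, because SAP 6.7 takes the last value before the very first study drug dose. The PK analyses and vital signs are also unaffected. Because the documents give no rate of unscheduled labs, the likelihoods and mean shifts are illustrations and not estimates. Confidence is medium, because the ADS Plan and the laboratory standard could not be read.

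**What to change.** Add one sentence to SAP 7.8.2:

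> An unscheduled laboratory value enters the by-time-point statistics of the previous scheduled time point only if no start of a new study treatment (first bupropion dose, first BI 1358894 dose, or Period T bupropion dose) lies between the two samples; otherwise it is listed and attributed to treatment by the time it was taken (Table 6.1: 1).

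This covers all three treatment starts and the parameters outside set B. If the ADS Plan or the laboratory standard already contains such a rule, stating it in 7.8.2 is enough.

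The cost is one sentence and one date/time comparison in the programming, with no new data or tables. The downside should be accepted openly. In subjects with later on-treatment labs, the values concerned would appear in no laboratory summary table. They would remain in the listings, in the flags for possibly clinically significant values and, if judged clinically relevant, in AE reporting. A value that is the subject's last on treatment would still enter the planned frequency table.

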### **7.8.3      Vital signs**

The analyses of vital signs (blood pressure, pulse rate) will be descriptive in nature. Descriptive statistics of vital signs over time and for the difference from baseline (see [Section 6.7](#)) will be provided.

Unscheduled measurements of vital signs will be assigned to planned time points in the same way as described above for laboratory data. However, for vital signs, descriptive statistics will be calculated by planned time point based on the last value of the subject at that planned time point (or assigned to that planned time point). If the time of measurement is missing for a scheduled post-baseline measurement, the scheduled measurement will be used in calculation of descriptive statistics (as time difference between scheduled and unscheduled cannot be assessed). Unscheduled measurements assigned to planned time point -336:00 will only be used in calculation of descriptive statistics if the measurement is taken before administration of first dose of BI 1358894 as it is planned for this time point.

If the time of measurement is missing for an unscheduled measurement, this measurement will be listed but will be ignored for the calculation of descriptive statistics.

Clinically relevant findings in vital signs data will be reported as baseline conditions (prior to first administration of study treatment) or as AEs (after first administration of study treatment) if judged clinically relevant by the investigator, and will be analyzed as such.

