| | 1 | -3:00 | | | X ¹¹ | | X | X | X |
| | | 0:00 | 08:00 | Administration of 150 mg Bupropion⁴ | | | | | |
| | | 1:00 | 09:00 | | X | | | | |
| | | 2:00 | 10:00 | 240 mL fluid intake | X | | | | |
| | | 3:00 | 11:00 | | X | | | | |
| | | 4:00 | 12:00 | 240 mL fluid intake thereafter Lunch ⁸ | X | | | | X |
| | | 5:00 | 13:00 | | X | | | | |
| | | 6:00 | 14:00 | | X | | | | |
| | | 7:00 | 15:00 | | X | | | | |
| | | 8:00 | 16:00 | Snack (voluntary) ⁸ | X | | | | |
| | | 10:00 | 18:00 | | X | | | | |
| | | 11:00 | 19:00 | Dinner | | | | | |
| | | 12:00 | 20:00 | | X | | | | X |
| | 2 | 24:00 | 08:00 | Breakfast ⁸ | X | B | X | X | X |
| | | 24:30 | 08:30 | Discharge from trial site | | | | | |
| 3 | 48:00 | 08:00 | | Ambulatory visit | X | | | | X |
| 4 | 72:00 | 08:00 | | Ambulatory visit | X | | | | X |
| 5 | 96:00 | 08:00 | | Ambulatory visit | X | | | | X |
| 6 | 120:00 | 08:00 | | Ambulatory visit | X | B ¹² | | | X |

FLOW CHART PERIOD T

| Visit | Day | Planned Time [h:min] relative to Bupropion | Approximate clock time of actual day ¹ [h:min] | Event and comment | PK _(plasma) for BI 1358894 ⁶ | Clinical laboratory tests ² | PK _(plasma) for Bupropion and metabolites ⁶ | Vital signs (BP, PR) ECG ³ | Physical /Neurological Examination | Questioning for AEs and concomitant therapy ⁷ |
|-------|-----|--|---|--|--|--|---|---------------------------------------|------------------------------------|--|
| 3 | -14 | -336:00 | 08:00 | Administration of 100 mg BI 1358894^{4,5} | X ¹⁵ | X ^{13, 14,15, 16} | | X ¹⁵ | X ¹⁵ | X |
| | | | 10:00 | Discharge | | | | X | | |
| | -13 | -312:00 | 08:00 | Ambulatory visit Administration of 100 mg BI 1358894⁴ | | | | | | X |
| | -12 | -288:00 | 08:00 | Ambulatory visit Administration of 100 mg BI 1358894⁴ | | | | | | X |
| | -11 | -264:00 | 08:00 | Ambulatory visit Administration of 100 mg BI 1358894⁴ | | | | | | X |
| | -10 | -240:00 | 08:00 | Ambulatory visit Administration of 100 mg BI 1358894⁴ | | | | | | X |
| | -9 | -216:00 | 08:00 | Ambulatory visit Administration of 100 mg BI 1358894⁴ | | | | | | X |
| | -8 | -192:00 | 08:00 | Ambulatory visit Administration of 100 mg BI 1358894⁴ | | | | | | X |
| | -7 | -168:00 | 08:00 | Ambulatory visit Administration of 100 mg BI 1358894⁴ | | | | | | X |
| | -6 | -144:00 | 08:00 | Ambulatory visit Administration of 100 mg BI 1358894⁴ | X ¹⁵ | B | | | | X |
| | -5 | -120:00 | 08:00 | Ambulatory visit Administration of 100 mg BI 1358894⁴ | | | | | | X |

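### In Period T, the last-value rule in SAP 7.8.3 lets a later unscheduled vital sign replace the pre-bupropion value and the 2-hour post-first-dose value in the by-time tables

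*SAP*

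**What the plan says.** SAP 7.8.3 takes its assignment rule from the laboratory section: "Unscheduled measurements of vital signs will be assigned to planned time points in the same way as described above for laboratory data". That rule, in SAP 7.8.2, regards unscheduled measurements as repeats, and "unscheduled measurements will be assigned to the planned time point of the previous scheduled measurement". It sets no limit on elapsed time and takes no account of doses given in between. Laboratory tables then use the worst value. For vital signs, "descriptive statistics will be calculated by planned time point based on the last value of the subject at that planned time point".

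One slot is protected: "Unscheduled measurements assigned to planned time point -336:00 will only be used in calculation of descriptive statistics if the measurement is taken before administration" of the first BI 1358894 dose. The reason given is that a pre-dose reading is what was planned there. Two further provisions deal with missing clock times. For an untimed unscheduled reading, "this measurement will be listed but will be ignored for the calculation of descriptive statistics". For a scheduled one: "If the time of measurement is missing for a scheduled post-baseline measurement, the scheduled measurement will be used in calculation of descriptive statistics".

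The Period T Flow Chart schedules vital signs before dosing on Day -14 (-336:00), at 10:00 that day ("10:00 | Discharge | | | | X"), on Day 1 at -0:30, and at 24:00 and 120:00, followed by the end-of-study examination. SAP 6.7 separately defines baseline, for every parameter, as the last available value before the very first dose of either drug.

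**The concern.** The reason given for protecting -336:00 applies equally to Visit 3 Day 1 -0:30, which is also a planned pre-dose reading, yet no restriction is written there. That row is the only scheduled vital-sign reading after two weeks of BI 1358894 and before bupropion is added. SAP 6.1 groups vital signs by period, so within Period T the planned time point is what separates a reading before bupropion from one after it. A reading filed in the wrong row loses that distinction.

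The 2-hour reading on Day -14 closes the in-house observation period after the first BI 1358894 dose. It is the only scheduled reading in the first hours after any BI 1358894 dose. No vital signs are scheduled again until Day 1 -0:30, so the rule can file a reading from many doses later in its place.

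Unscheduled vital signs may well be prompted by symptoms. If so, replacement would not be random with respect to the value measured.

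**Working it through.** The plan states no figure to reproduce here. The check applies the written rules to the Flow Chart times and then sizes the effect under stated assumptions.

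**1. Slots.** Hours are relative to bupropion at Visit 3. Dosing on Day -14 is at 08:00 = -336:00, so the 10:00 reading is at -336 + 2 = -334:00. The Period T slots up to Day 6 are -336:00, -334:00, -0:30, 24:00 and 120:00.

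**2. Rule.** File each timed unscheduled reading under the latest earlier slot. At -336:00, discard it if it was taken after dosing. Keep the last value in each slot.

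**3. Result for a single unscheduled reading.**

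| Taken at | Filed under | Value tabulated in that slot |
|---|---|---|
| -335 h | -336:00 | scheduled (protected) |
| -333, -200 or -24 h | -334:00 | unscheduled |
| -0.25 h | -0:30 | unscheduled (still pre-dose, correctly filed) |
| +3, +12 or +23 h | -0:30 | unscheduled (post-bupropion) |

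**4. Window lengths.**
- Pre-bupropion slot: 24 - (-0.5) = 24.5 h. The first 0.5 h precedes dosing and is filed correctly, so 24.5 - 0.5 = 24 h is misfiled.
- 2-hour slot: -0.5 - (-334) = 333.5 h, or 333.5/24 = 13.9 days. It spans the doses on Days -13 to -1.

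**5. Comparison with SAP Table 6.1: 1.** The combined BI 1358894 + bupropion phase starts at bupropion dosing on Visit 3 Day 1. A reading at +3 h, close to the bupropion tmax of about 2.5 to 3 h in Protocol 1.2.2, belongs to that phase. SAP 7.8.3 tabulates it at -0:30, before the phase starts. Readings from the 333.5 h window all stay within the BI 1358894 phase that ends at bupropion dosing, so they cross no phase boundary. What is wrong there is the time label: a reading up to 13.9 days later is not a repeat of the 2-hour value.

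**6. Size (assumed).** The documents give no count of unscheduled readings. With 18 subjects (Protocol 7.7), if k values are replaced and each differs by d in the same direction, the row mean moves by k × d/18.
- k = 1, d = 5: 5/18 = 0.28
- k = 1, d = 20: 20/18 = 1.11
- k = 3, d = 20: 60/18 = 3.33

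Units are mmHg or bpm. With no timed unscheduled reading, the shift is zero.

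**The case against.** The best defence is that little depends on these rows. The tables are descriptive, with no hypothesis test. SAP 7 lists every individual value, and clinically relevant vital-sign findings after first dosing are reported and analysed as AEs. SAP 6.2 sends time-window deviations to the Report Planning Meeting, and SAP 6.1 refers technical detail to an ADS Plan that is not among the documents and might add restrictions. Treating unscheduled readings as repeats is also a stated convention. All of this stands and limits the importance of the point. It does not correct the written rule, which places a post-bupropion reading in a pre-bupropion row and departs from the SAP's own reasoning for -336:00.

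A reader might draw three stronger conclusions that the documents do not support:

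- *The Period R baseline is shifted.* It is not. SAP 6.7 fixes baseline before the first dose, which in this R-T sequence is the first bupropion dose. SAP 7.8.3 merely omits to say how the Visit 2 Day 1 -3:00 row relates to that value.
- *The 2-hour reading is the only one within 24 h of a BI 1358894 dose.* The Day 1 -0:30 reading falls 24 - 0.5 = 23.5 h after the Day -1 dose.
- *Post-dose change is necessarily understated.* Differences are taken from the SAP 6.7 baseline, so a contaminated -0:30 row leaves the changes at 24:00 and 120:00 as they were. A high misfiled reading would show as a larger change in the -0:30 row, mislabelled but not hidden.

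**Conclusion.** The rule is wrong as written for one slot and too loose for another, both in Period T. At Day 1 -0:30, timed unscheduled readings from the 24 h after bupropion replace the pre-dose value and enter no post-dose row, contrary to the phase boundary in Table 6.1: 1. At the 2-hour slot on Day -14, readings from the next 333.5 h replace a value they do not repeat; the phase is right but the time resolution is lost.

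The point is minor. It affects only descriptive vital-sign summaries, and only if timed unscheduled readings occur. Under the assumptions above, a row mean moves by 0.28 to 3.33 mmHg or bpm. The SAP 6.7 baseline, the listings, AE reporting and the PK results are unaffected. The conclusion rests on the SAP text alone; the ADS Plan could already contain a restriction, but the SAP states none.

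**What to change.** In SAP 7.8.3:

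1. Extend the -336:00 sentence to Visit 3 Day 1 -0:30, so that an unscheduled value enters the statistics there only if taken before that day's dosing.
2. State that the Visit 2 Day 1 -3:00 row uses the pre-dose baseline value defined in SAP 6.7.
3. Let an unscheduled reading replace the 2-hour value on Day -14 only if it is a same-session repeat or the scheduled value is missing. Define same-session: the ±30 min that Protocol 6.1 allows for vital signs on Day 1 is a starting point, since 6.1 gives no vital-sign window for Day -14.

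Readings excluded from a row remain in the listings. A per-subject minimum and maximum row by analysis phase would also bring them into a summary table, but that is optional. The cost is three sentences and one derivation rule in the analysis data set, with no new data. If the ADS Plan already contains these restrictions, move them into the SAP text.
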